Adverse events	Collect continuously throughout the study. Adverse events that started during the previous study and are ongoing at the time the patient signs the written informed consent should be reported in this study.					
Concomitant medications	Collect continuously throughout the study.					
Complete physical examination			X			X
Extended neurological examination ^d			X			X
Abbreviated physical examination	X					
	Before and after each infusion					
Weight ^e	Before each infusion					
Height		X		X		X
Vital sign measurements (blood pressure, heart rate, respiratory rate, temperature) ^f	Before and 1 hour (± 10 minutes) after each infusion.					
Clinical laboratory tests (clinical chemistry, hematology, LFTs, coagulation, urinalysis)		X		X		X
Hematology, hemoglobin level and platelet count	During the study period, for the switch from Process B to Process C ^g or from Process C ^h to Process C ^h , 2 samples will be taken during an infusion 3 months after introducing the new process, one for differential hematology and the other for hemoglobin and platelet count at least 24 hours and up to 2 weeks apart.					

Study period		Treatment					Post treatment	
Note: The visit schedule is calculated in reference to the first infusion of the patient's previous study. The ± 14 day window applies only to assessments not linked to the time of the infusion (eg, abbreviated physical exams, vital signs), the Q2W visit window of ± 3 days remains.								
Visit/timing	Every 2 weeks (± 3 days)	QV ^a (± 14 days)	Study completion, patient discontinuation or withdrawal ^b	Safety follow-up phone call ^c				
Year 6	W274	W288	W300	W312				
Year 7	W326	W340	W352	W364				
Year 8	W378	W392	W404	W416				
Year 9	W430	W444	W456	W468				
Urine β -HCG pregnancy test (only women of childbearing potential)	Every 4 weeks					X		
Electrocardiogram ^{f, g}					X		X	
Safety biomarkers (hsCRP, iron, ferritin, calcitonin)		X			X		X	
Abdominal MRI (liver and spleen volumes)				X			X	
Chest HRCT			X				X	
Pulmonary function tests (FVC, FEV ₁ , DLCO, TLC) ^h				X			X	
Physician global assessment				X			X	
Efficacy biomarkers (serum chitotriosidase, CCL18)					X		X	
Fasting lipids (total cholesterol, HDL, LDL, VLDL, triglycerides, ApoB, ApoA1, lipoprotein [a])					X		X	
Metabolite levels in plasma (ceramide, lyso-sphingomyelin)					X		X	
Patient photographs (optional)					X			
Photographs (eg, abdominal) will be taken on patients who volunteer to provide visual context of the disease.								

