8.1.5 Dosing delays or missed doses

Dose reintroduction regimens may be required for patients who have missed more than 1 dose between studies or during this study (LTS13632), depending on their usual dose. For patients receiving home infusions who have missed 2 or fewer doses, the investigator can decide whether reintroduction should occur at the hospital/study site via home infusion. For patients who have missed 3 or more doses ≥ 0.6 mg/kg, reintroduction of olipudase alfa should occur at the hospital/study site. If the site visit is not possible due to site closure or extenuating circumstances that prevent an in-person site visit (eg, during COVID-19 pandemic), reintroduction may be done via home infusion, if the patient has previously been approved for home infusion.

Patients who require dose reintroduction will have these assessments at each infusion until reaching their usual dose of olipudase alfa:

- Before infusion: vital sign measurements, liver function tests (LFTs), hematology tests and safety biomarkers.
- Immediately after infusion: vital sign measurements.
- 24 hours after infusion: vital sign measurements, LFTs, hematology and safety biomarkers
- 48 hours after infusion: vital sign measurements, LFTs and safety biomarkers.

The 48 hours post-infusion assessments will no longer be assessed after the cutoff date for a planned second database lock of the study for purpose of regulatory submissions in 2021.

During the dose escalation period, for transaminases assessed after infusion, if any AST or ALT value is $>2x$ baseline and $>ULN$, the test should be repeated prior to the next scheduled infusion. Depending on the test results, the dose can be adjusted (repeated or reduced) or treatment can be withheld to allow additional transaminase monitoring, based on the physician's clinical judgment.

Baseline is defined as the following:

- For initial dose escalation: last values prior to first dose of olipudase alfa
- For dose re-escalation: last values prior to the first re-escalation dose

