9.5 SAMPLED BLOOD VOLUME

For all pediatric patients, no more than 7 mL/kg of blood will be collected during any 8-week period. Additional blood samples may be collected at the investigator's discretion for patient safety monitoring.

If a PK or IgG sample collection for the planned introduction of drug product from Process C(█) was erroneously taken, the future sample collection will be adjusted according to the blood volume allowed per each age cohort in order to avoid excessive blood withdrawal. For specific details, please refer to Study Manual.

[Table 17](#) shows the approximate sampled blood volume in patients ages 12 to <18 years old in the first 5 years.

Table 17 - Approximate sampled blood volume in patients ages 12 to <18 years in the first 5 years

Assessment	Volume (mL) per sample	Number of samples per year	Total (mL) per year
Liver function, clinical chemistry, and lipid profile	5.0	4	20.0
Hematology	2.0	4	8.0
Coagulation	3.6	4	14.4
Safety biomarkers	6.5	4	26.0
Efficacy biomarkers	10.0	4	40.0
Serum bone-specific AP and C-telopeptide	2.5	4	10.0
Metabolites in plasma and/or DBS	3.2	4	12.8
Anti-olipudase alfa IgG and neutralizing antibodies in IgG-positive patients	3.5	4	14.0
Olipudase alfa pharmacokinetics	1.5	7	10.5
		Approximate total per year	155.7
		Approximate total per 5 years	778.5

AP=alkaline phosphatase

Table 18, Table 19 show the additional approximate sampled blood volume in patients ages 12 to <18 years old with an olipudase alfa manufacturing scale change or manufacturing process update respectively. Not all of the patients will be exposed to both changes; therefore, blood volume would be calculated individually. To avoid excessive blood volume withdrawn, if similar assessment is regularly scheduled (IgG, PK or hematology and coagulation) in the same month, priority is given to manufacturing scale or updated manufacturing process update assessments and the regular similar assessments may be canceled.

Table 18 - Additional approximate sampled blood volume in patients ages 12 to <18 years with an olipudase alfa manufacturing scale change

Assessment	Volume (mL) per sample	Number of samples	Total (mL)
Anti-olipudase alfa IgG and neutralizing antibodies in IgG-positive patients	3.5	1 sample per month for 6 months	21.0
Olipudase alfa pharmacokinetics - prior to manufacturing scale change	1.5	7	10.5
Olipudase alfa pharmacokinetics - post manufacturing scale change	1.5	7	10.5
Approximate additional volume per study			42.0

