Table 19 - Additional approximate sampled blood volume in patients ages 12 to <18 years with the olipudase alfa updated manufacturing process

Assessment	Volume (mL) per sample	Number of samples	Total (mL)
Anti-olipudase alfa IgG and neutralizing antibodies in IgG-positive patients	3.5	1 sample per month for 6 months	21.0
Olipudase alfa pharmacokinetics – Second infusion on updated process	1.5	7	10.5
Hematology samples 3 months after first infusion on updated process	2	1	2
Coagulation and platelet samples 3 months after first infusion on updated process	3.6	1	3.6
Approximate additional volume per study			37.1

Table 20 shows the approximate sampled blood volume in patients ages 12 to <18 years old beyond 5 years.

Table 20 - Approximate sampled blood volume in patients ages 12 to <18 years beyond 5 years

Assessment	Volume (mL) per sample	Number of samples per year	Total (mL) per year
Liver function, clinical chemistry, and lipid profile	5	2	10.0
Hematology	3.6	2	7.2
Safety biomarkers	6.5	2	13.0
Efficacy biomarkers	10	1	10.0
Metabolites in plasma and/or DBS	3.2	1	3.2

Assessment	Volume (mL) per sample	Number of samples per year	Total (mL) per year
Approximate total per year, beyond 5 years			43.4
Approximate total per 4 years, beyond 5 years			173.6

Table 21 shows the approximate sampled blood volume in the child cohort (6 to <12 years old) and in patients ages 3 to <6 years old in the first 5 years.

Table 21 - Approximate sampled blood volume in patients in the child cohort (6 to <12 years) and in patients ages 3 to <6 years in the first 5 years

Assessment	Volume (mL) per sample	Number of samples per year	Total (mL) per year
Liver function, clinical chemistry, and lipid profile	4.0	4	16.0
Hematology	1.2	4	4.8
Coagulation	2.8	4	11.2
Safety biomarkers	6.2	4	24.8
Efficacy biomarkers	5.1	4	20.4
Serum bone-specific AP and C-telopeptide	2.2	4	8.8
Metabolites in plasma and/or DBS	1.5	4	6.0
Anti-olipudase alfa IgG and neutralizing antibodies in IgG-positive patients	1.1	4	4.4
Olipudase alfa pharmacokinetics	1.5	6	9.0
		Approximate total per year	105.4
		Approximate total per 5 years	527.0

AP=alkaline phosphatase

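### The beyond-5-year pediatric blood tables leave out one tube, and the mandated dose-reintroduction draws are in no table although a long reintroduction could exceed the 7 mL/kg limit in a very light child

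*Protocol*

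**What the plan says.** Section 9.5 states the limit without exception for scheduled draws: "For all pediatric patients, no more than 7 mL/kg of blood will be collected during any 8-week period". The next sentence adds: "Additional blood samples may be collected at the investigator's discretion for patient safety monitoring".

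Section 8.1.5 makes the reintroduction draws compulsory: "Patients who require dose reintroduction will have these assessments at each infusion until reaching their usual dose of olipudase alfa". The content is:

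- "Before infusion: vital sign measurements, liver function tests (LFTs), hematology tests and safety biomarkers"
- "24 hours after infusion: vital sign measurements, LFTs, hematology and safety biomarkers"
- "48 hours after infusion: vital sign measurements, LFTs and safety biomarkers", a draw that ends after the cutoff for the second database lock.

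The lists do not agree across the protocol. Section 1 includes hematology at both 24 h and 48 h; Section 8.1.5 includes it at 24 h only; the synopsis includes it at neither.

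Tables 17 to 28 budget routine sampling and the extra draws for a manufacturing scale change or process update, by age band. Table 29 budgets draws after hypersensitivity-type reactions. None has a reintroduction row. The rule that a regular sample may be cancelled covers only manufacturing changes.

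For the later period, for example "Table 20 - Approximate sampled blood volume in patients ages 12 to <18 years beyond 5 years", each table has one hematology row and no coagulation row. The flow charts beyond Year 5 still schedule "Clinical laboratory tests (clinical chemistry, hematology, LFTs, coagulation, urinalysis".

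**The concern.** The 9.5 tables are the protocol's account of how much blood is taken from children, and the protocol goes to ethics committees. If a tube is missing, the stated totals are too low. If a compulsory set of draws is missing, nobody has checked it against the limit that opens the same section. Because the tables give yearly or per-study totals, they cannot show compliance with an 8-week limit in any case.

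Where the two rules collide, a site must either pass the limit or omit a required sample. Section 8.1.5 ties dose decisions during escalation to post-infusion transaminases, so the omission would matter.

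**Working it through.** **1. Tables beyond 5 years**

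The printed totals reproduce from their rows (mL per sample × samples per year):

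- Table 20: 5×2 + 3.6×2 + 6.5×2 + 10×1 + 3.2×1 = 43.4; × 4 years = 173.6
- Table 24: 4×2 + 2.8×2 + 6.2×2 + 5.1×1 + 1.5×1 = 32.6; × 4 = 130.4
- Table 28: 4×2 + 2.8×2 + 4×2 + 3.7×1 + 1.5×1 = 26.8; × 4 = 107.2

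The sums are right. The row content is not:

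| Age band | Hematology, first 5 years | Coagulation, first 5 years | Hematology row, beyond 5 years |
|---|---|---|---|
| 12 to <18 (Tables 17, 20) | 2.0 mL | 3.6 mL | 3.6 mL |
| 3 to <12 (Tables 21, 24) | 1.2 mL | 2.8 mL | 2.8 mL |
| birth to ≤2 (Tables 25, 28) | 1.2 mL | 2.8 mL | 2.8 mL |

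Tables 19, 23 and 27 carry the same hematology and coagulation volumes as the first-5-year tables. Restoring the missing tube twice a year:

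- Table 20: 43.4 + 2×2.0 = 47.4 mL/year (+9.2%); 189.6 per 4 years
- Table 24: 32.6 + 2×1.2 = 35.0 (+7.4%); 140.0
- Table 28: 26.8 + 2×1.2 = 29.2 (+9.0%); 116.8

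The shortfall is the same whether the row is a mislabelled coagulation tube, or hematology at the wrong volume with coagulation dropped.

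**2. Reintroduction draws**

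Inputs are the first-5-year tube volumes: liver/chemistry/lipid 4.0 mL in both younger bands, hematology 1.2 mL in both, safety biomarkers 4.0 mL (birth to ≤2) and 6.2 mL (3 to <12). Infusions are every 2 weeks, so four fall in 8 weeks. Threshold weight = total mL ÷ 7.

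- Birth to ≤2: (4.0 + 1.2 + 4.0) = 9.2 mL per draw; × 2 draws × 4 infusions = 73.6 mL; ÷ 7 = 10.5 kg
- 3 to <12: (4.0 + 1.2 + 6.2) = 11.4 mL per draw; × 2 × 4 = 91.2 mL; ÷ 7 = 13.0 kg

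The documents give no LFT-only tube volume, no body weights and no exact number of reintroduction infusions, so the range matters:

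| Case | birth to ≤2 | 3 to <12 |
|---|---|---|
| Base: pre + 24 h, four infusions, 4.0 mL tube | 10.5 kg | 13.0 kg |
| No hematology at 24 h (synopsis) | 68.8 mL, 9.8 kg | 86.4 mL, 12.3 kg |
| LFT-only tube of 1 to 3 mL (assumption) | 7.1 to 9.4 kg | 9.6 to 11.9 kg |
| Three infusions | 55.2 mL, 7.9 kg | 68.4 mL, 9.8 kg |
| Two infusions | 36.8 mL, 5.3 kg | 45.6 mL, 6.5 kg |
| Base + yearly visit with PK | 92.4 mL, 13.2 kg | 112.9 mL, 16.1 kg |
| Before the cutoff, 48 h draw per 8.1.5 | 105.6 mL, 15.1 kg | 132.0 mL, 18.9 kg |
| Before the cutoff, 48 h draw per Section 1 | 110.4 mL, 15.8 kg | 136.8 mL, 19.5 kg |

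The yearly-visit row lets the pre-infusion draw serve both purposes and adds only the remaining tubes (11.3 or 12.7 mL) and PK (7.5 or 9.0 mL). For comparison, the largest routine visit with PK is 28.0 or 33.1 mL and reaches the limit only below 4.0 or 4.7 kg.

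**The case against.** **Four infusions is an assumption.** Section 8.1.1 leaves the detail after three or more missed doses to the study manual, and after two missed doses reintroduction is short and stays well inside the limit. This stands as a condition. Four is nevertheless plausible. Section 8.1.1 has 0.3 mg/kg given and then repeated along the original escalation schedule, and Sections 4.1 and 10.5.1.3.2.3 show the adult study passing through 0.6 to 2.0 mg/kg on the way to 3.0 mg/kg. If pediatric escalation is similar, at least four infusions precede a usual dose of 3.0 mg/kg.

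**The 4.0 mL tube is an upper bound,** since it also covers chemistry and lipids. This stands, and the range above shows its effect.

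**The youngest band is nearly empty.** The amendment 06 rationale (January 2021) says analyses through 52 weeks of treatment were complete for all patients. Adding about 63 weeks to April 2022 puts every child about 115 weeks, or 2.2 years, past first infusion. So few if any current patients would be in the birth to ≤2 group. Table 28 cannot describe current age at all, because a patient beyond 5 years of treatment is older than 5.

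**Investigator discretion.** Section 10.4.1 speaks of appropriate monitoring at reintroduction as a matter for the investigator, and 9.5 allows discretionary safety samples. Neither exempts these draws: 10.4.1 itself separates the assessments that will be repeated under 8.1.5 from additional ones the investigator may choose.

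**The understatement may be offset.** Tables 9 and 10 no longer list troponin I, IL-6 and IL-8 as routine safety biomarkers, yet the tube volume stays at 6.5, 6.2 and 4.0 mL. A smaller tube would reduce the gap; cancelling it fully would need 2.0, 1.2 and 1.2 mL less per sample (31%, 19% and 30%). The documents do not say, so the volume needs confirming.

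**Conclusion.** Two omissions stand. Tables 20, 24 and 28 are short by 4.0, 2.4 and 2.4 mL/year at the protocol's own tube volumes, a 7 to 9% understatement that does not itself threaten the limit. The mandated reintroduction draws are unbudgeted and, under the schedule after the cutoff, could exceed 7 mL/kg below about 10.5 kg (birth to ≤2) or 13.0 kg (3 to <12). Those weights rest on four infusions in 8 weeks and a 4.0 mL tube; the plausible range runs from about 7 to 13 kg and about 10 to 16 kg.

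Three stronger readings are tempting, and the documents do not support them:

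- That a site can never follow both rules. Above the threshold weight, and in short reintroductions, both can be met.
- That the 15 to 20 kg thresholds describe current practice. They belong to the 48 h draw, which ends at a cutoff planned for 2021 submissions; amendment 07 is dated April 2022.
- That the protocol regards transaminase risk as highest during re-escalation. It calls elevation during dose escalation an important identified risk and does not rank it.

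This is worth correcting in the next amendment. It does not bear on the trial's analyses.

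**What to change.** - In Tables 20, 24 and 28, show hematology and coagulation as separate rows, confirm the safety-biomarker volume beyond Year 5, and restate the totals. With volumes unchanged they are 47.4, 35.0 and 29.2 mL/year (189.6, 140.0 and 116.8 mL per 4 years).
- State whether the age bands mean current age or age at entry to the original study. Table 28 makes sense only under the latter.
- Add a reintroduction row to the pediatric tables, per infusion and per 8 weeks, using the actual tube volumes and showing the body weight at which the limit is reached.
- Reconcile the synopsis, Section 1 and Section 8.1.5 on which draws include hematology, and reconcile them with Section 9.5 so that the mandated sampling and the 7 mL/kg limit are consistent. Which passage governs is for the sponsor to decide.

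The cost is a table correction in the next amendment and a line in the study manual. No new procedure or sample is added.

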9.6 FUTURE USE OF SAMPLES

For patients who have consented to it, left over samples following testing may be used for other research purposes (excluding genetic analysis) related to ASMD. These samples will be stored for 15 years after end of the study in compliance with applicable country-specific regulations.

These other research analyses will help to understand either disease subtypes or drug response, or to develop and/or validate a bioassay method, or to identify new drug targets or biomarkers.

These samples will remain labeled with the same identifiers as the ones used during the study (ie, subject ID). They will be transferred to a Sanofi site (or a subcontractor site) which can be located outside of the country where the study is conducted. The sponsor has included safeguards for protecting subject confidentiality and personal data ([Section 14.3](#) and [Section 14.5](#), respectively).

10 STUDY PROCEDURES

10.1 VISIT SCHEDULE

Section 1.1 through Section 1.5 summarize the schedules of study events for all patients enrolled into this study. Individual assessments are described in Section 9.

10.2 STUDY PROCEDURES

Infusions will take place at the study site, or for some patients, at home.

10.2.1 Home infusions

Home infusion may be possible. Patients must meet the eligibility requirements outlined below. In addition, the investigator and the sponsor must agree that home infusion is appropriate. To receive home infusions, the following criteria must be met:

- The investigator must agree in writing that home infusion is appropriate for the patient.
- The patient, or the pediatric patient's parent(s) or legal guardian(s), must be willing and able to comply with home infusion procedures.
- The patient must, in the investigator's (or designee's) opinion, have been clinically stable with no history of moderate or severe IARs for at least 6 months, and must be on a stable olipudase alfa dose. No infusion rate increases will be allowed while a patient is receiving home infusions.
- The patient must have no ongoing (not yet recovered) SAEs that, in the opinion of the investigator, may affect the patient's ability to tolerate the infusion.
- Home infusion infrastructure, resources, and procedures must be established and available according to applicable regional regulations.
- For patients experiencing an IAR while being infused at home, the investigator should assess whether or not it is safe for the patient to continue to be treated via home infusion or return to the study site for their following infusion and when the patient would be ready to resume home infusion. In case home infusion continues, the investigator will guide the home infusion staff on the measures to be followed for subsequent infusion to manage the IAR (eg, infusion interruption, premedication, change the infusion rate, etc. See Treatment of infusion-associated reactions in Section 8.6.1).
- If recurrent IARs or hypersensitivity reactions occur, the investigator should assess whether or not it is safe for the patient to continue to be treated via home infusion.
- If a severe hypersensitivity reaction or an anaphylaxis reaction occurs, during an infusion given at home, treatment will be discontinued immediately, and appropriate medical treatment will be initiated. The patient will return to the study site for further management

until the investigator agrees with the sponsor that it is safe for the patient to continue to be treated via home infusion. See [Section 8.6](#) for details on severe hypersensitivity and anaphylaxis management.

- For the switch from Process C(█) IMP to Process C(█) IMP, if the site visit is possible, the patient should receive the first infusion at the site. However, if the site visit is not possible during a regional or national emergency declared by a governmental agency such as the COVID-19 pandemic due to site closure or extenuating circumstances that prevent an in-person site visit, the first infusion of the Process C(█) IMP is allowed during home infusion for eligible patients in agreement between the Sponsor and the Investigator in compliance with applicable country-specific regulations.
- Prior to beginning home infusions, the home infusion staff, including new staff members, must have been appropriately trained and/or licensed, if applicable, on proper procedures to prepare and administer infusions, monitor patients, document procedures, and report to site on a timely basis.
- The home infusion staff must have access to and be trained on proper use of safety equipment, including, but not limited to, cardiopulmonary resuscitation equipment.
- Home infusion staff must keep source documentation of the infusion, including documentation of any AEs. Home infusion staff must be amenable to providing specific source documentation to Sanofi Genzyme and agree to be monitored. The Principal Investigator is still responsible for all study procedures and patient's safety even when delegating infusion responsibilities to the home care company.
- An additional questionnaire about home infusion experience may be added any time before end of the study for patients who received home infusion treatment for total time of at least of one year.

10.2.2 Alcohol consumption

Patients must be willing to abstain from the use of alcohol for 1 day prior to and 3 days after each study drug infusion (see [Section 7.2](#)).

Patients will be counseled to limit alcohol consumption during the study:

- Male patients to a maximum of 30 grams of alcohol per day (2 drinks/day).
- Female patients to a maximum of 15 grams of alcohol per day (1 drink/day).

Patients who do not limit alcohol can be discontinued from the study according to investigator's discretion.

